## **7.1 Scheduled Study Visits**

### **7.1.1 Screening (-30 days to Day 1)**

The following will take place during the Screening visit, which will occur within 30 days prior to Day 1, or the visit may be combined with Day 1 (preferred):

- Informed consent
- Demographics
- Review of eligibility criteria
- Medical history
- Physical exam
- Vital signs
- Urine pregnancy test for females of childbearing potential
- Prior and concomitant medications review

Screening and Day 1 Visits are encouraged to be combined into the same day to complete 1 set of procedures.

### 7.1.2 Day 1

If the subject had a separate Screening visit, the following procedures will take place during the Day 1 visit and ***before*** study vaccine administration:

- Updated medical history
- Confirm Inclusion/Exclusion criteria are met
- Targeted physical examination, if indicated by updated medical history
- Vital signs
- Biological specimen collection for clinical laboratory tests:
  - Blood for hematology and chemistry
  - Urine for urinalysis
  - Serum for immunogenicity
- Urine pregnancy test for females of childbearing potential
- Prior and concomitant medications review
- Randomization

All eligible, consented, and randomized subjects will be vaccinated at the Day 1 Baseline visit.

- Study vaccine administration, either VAX-31 or PCV20

The following procedures will take place during the visit and ***after*** study vaccine administration:

- Acute observation for at least 30 minutes after vaccine administration
- Vital signs collected at least 30 minutes after vaccine administration
- AE (solicited and unsolicited) and SAE evaluation
- Review of concomitant medications taken after vaccination
- Instructions on completion of a diary (login to new account for electronic diary), use of a ruler and thermometer

### **7.1.3 Day 8 (+3 days)**

The following procedures will take place at this visit:

- Visual inspection of injection site location
- Review of diary data with the subject; Investigator's assessment of severity and relationship to study vaccine
- Review of concomitant medications
- AE (solicited and unsolicited) and SAE evaluation

### **7.1.4 Day 15 (+3 days)**

This visit is a follow-up phone call for safety evaluation. The following procedures will take place at this visit:

- Review of concomitant medications
- AE (unsolicited) and SAE evaluation

### **7.1.5 Month 1 (30 days after Day 1, ±3 days)**

The following procedures will take place during this visit:

- Review of concomitant medications
- AE (unsolicited) and SAE evaluation
- Biological specimen collection for clinical laboratory tests:
  - Blood for hematology and chemistry
  - Urine for urinalysis
  - Serum for immunogenicity

### **7.1.6 Months 2, 3, 4, 5, and 6 (60 to 180 days after Day 1 [±5 days])**

These visits are follow-up phone calls for safety evaluation. The following procedures will take place at each visit:

- SAE, NOCI, and MAAE evaluation
- Review of concomitant medications or vaccines potentially related to SAE, NOCI, MAAE, or prohibited medications

## 7.2 Early Termination Visit

All subjects who discontinue study participation before the Month 6 visit will be requested to undergo an Early Termination (ET) visit.

- Review of diary data with the subject; Investigator's assessment of severity and relationship to study vaccine (if ET is within 7 days)
- Review of unsolicited AE and SAE
- Review of concomitant medications associated with new or ongoing AE and any SAE
- Biological specimen collection for clinical laboratory tests (if ET is after Day 8 and before Month 1)
  - Blood for hematology and chemistry
  - Urine for urinalysis
  - Serum for immunogenicity

## 7.3 Unscheduled Visits

Any study procedure, excluding study vaccination, may be conducted at an unscheduled visit as needed. Examples include repeat specimen collection and additional safety follow-up for an AE.

# 8. Safety

## 8.1 Definitions

### 8.1.1 Adverse Event

An AE is any untoward medical occurrence in a study subject, regardless of the suspected causal relationship with study vaccine. The definition of an AE includes:

- A new-onset symptom or disease
- An exacerbation of a pre-existing symptom or disease
- A new-onset clinical laboratory abnormality considered by the Investigator to be clinically significant
- A new-onset symptom or disease that occurs as a result of a protocol-specified procedure

The definition of an AE does **not** include:

- A pre-existing symptom or disease that does not worsen during the study (even if first disclosed by the subject after the start of the study)

- A medical or surgical intervention such as surgery, endoscopy, tooth extraction, or transfusion (although the condition leading to the procedure or a complication from the procedure may be an AE)
- An uncomplicated pregnancy
- A dosing error without any resulting signs or symptoms
- Any other situation where an untoward medical occurrence has not occurred (e.g., hospitalization for cosmetic elective surgery or social admissions)

The definition of a treatment emergent adverse event (TEAE) is an event that occurs after vaccination and within 30 days after vaccination (i.e., excluding those after a subject has given informed consent, but before vaccination).

The definition of a medically attended adverse event (MAAE) includes:

- A new onset or worsening of a condition that prompts the subject to seek unplanned medical advice at a physician's office, urgent care center, or Emergency Department

The definition of a new onset of chronic illness (NOCI) includes:

- A new onset of a disease or condition that requires ongoing medical attention and/or limits activity of daily living, e.g., heart disease, cancer, diabetes

The Investigator will attempt to establish a diagnosis based on signs, symptoms, and other clinical information. Whenever possible, the Investigator will report an AE as a diagnosis rather than 1 or more signs or symptoms. If a clinically significant laboratory abnormality meets the definition of an AE, a diagnosis or clinical signs and symptoms rather than the abnormal clinical laboratory finding should be reported if possible. If no diagnosis is known and clinical signs and symptoms are not present, but the laboratory abnormality is clinically significant by itself, then it should be reported as the AE.

### **8.1.2     Solicited Adverse Event**

A solicited AE is a protocol-specified AE about which the Investigator or designee proactively asks the subject during a protocol-specified time period. Solicited AE for this study are local events of pain, erythema (redness), and edema (swelling) at the injection site, and systemic events of fever (oral temperature  $\geq 100.4^{\circ}\text{F}$ ), fatigue, headache, muscle pain, and joint pain.

### **8.1.3 Unsolicited Adverse Event**

An unsolicited AE is an AE that is spontaneously reported by the subject or discovered by the Investigator. New onset of chronic illness(es) would be recorded as part of the collection of unsolicited AE as specified in the visit procedures. Unsolicited AE will be collected separately from solicited AE. Solicited AE occurring or persisting beyond the solicitation period or which meet SAE/NOCI/MAAE criteria are also recorded as unsolicited AE.

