## **6.12 Unsolicited Adverse Events**

Unsolicited AE (any AE not listed in the diary) will be collected for this study. Details regarding definitions, evaluation, reporting periods, and documentation are outlined in Section 8.

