3.2. Safety Variables

Safety assessments performed during the study included solicited AE up to Day 8 and monitoring of unsolicited adverse events, physical examinations, measurement of vital signs, clinical laboratory evaluations including hematology, serum chemistry, and urinalysis. See Section 6.2.5 for the definition of age group.

The primary endpoints are:

- Percentage of subjects reporting solicited local reactions within 7 days after vaccination (redness, swelling, and pain at injection site) in each age group.
- Percentage of subjects reporting solicited systemic events within 7 days after vaccination (fever, headache, fatigue, muscle pain, and joint pain) in each age group.
- Percentage of subjects reporting unsolicited AE within 1 month after vaccination in each age group.
- Percentage of subjects reporting SAEs within 6 months after vaccination.
- Percentage of subjects reporting NOCIs within 6 months after vaccination.
- Percentage of subjects reporting MAAEs within 6 months after vaccination.

The secondary endpoint related to Safety assessments is:

- Safety: Percentage of participants with laboratory value abnormalities and/or potentially clinically significant laboratory values at 1 month after vaccination.
- Safety: Change from baseline in laboratory parameters at 1 month (30 days) after vaccination

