5.2. Data Conventions

The following conventions will be used:

- **Period definition:**
 - **Screening Period:** The period prior to Day 1 visit.
 - **Treatment and Observation:** The period from date of vaccine administration to Month 1 visit (included).
 - **Follow-up:** The period from Month 1 visit (excluded) to Month 6 visit.
- **Visits:**
 - **Study day 1:** The date of study vaccine administration.
 - **End of Treatment Visit:** The Month 1 visit, or the early discontinuation visit for subjects who withdraw study prior to Month 1 visit.
 - **End of Study Visit:** The last recorded visit date.
 - **Unscheduled visits:** Unscheduled visits results will be listed, but not included in tables or graphs. Rules to map unscheduled visit to analysis visit are defined in Section 5.5.
- **Baseline characteristics and change from baseline:**
 - Weight values recorded in pounds will be converted to kilograms using the following formula: kilograms = pounds/2.2046.
 - Height values recorded in inches will be converted to centimeters using the following formula: centimeters = inches*2.54.
 - Duration on study (weeks) = (Last visit date – randomization date + 1) / 7.
 - (Absolute) Change from baseline = Value at the time point – Baseline value.
- **Adverse events:**
 - **Solicited Adverse Events** will be analyzed using the nominal visit (i.e. the page) on which they were recorded and not according to the date they were entered.

- **Solicited Adverse Events continuing beyond 7 days:** Solicited AEs continuing beyond 7 days will be reported in the “Adverse Events (Unsolicited)” page as per Case Report Form (CRF) Completion guidelines and will be identified programmatically as all unsolicited adverse events with answer ‘Yes’ to the question ‘Is this a Prolonged Solicited Adverse Event?’. The corresponding question in the diary page (‘Were any of the above symptoms continuing after Day 7?’) will not be used as it is expected that both sources will be reconciled before iDBL so that only the unsolicited page can be used for the analysis.
- **Immunogenicity:**
 - OPA results are reported as titer and IgG results are reported as concentration
 - **GMC [or GMT]:** The geometric mean concentration (or titer) = antilog10 (LSMeans [$\log_{10} x$]), where x is the assay result and LSMeans is the least square means calculated by the model.

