6.5.1.2. Unsolicited Adverse Events

An unsolicited AE is an AE that is spontaneously reported by the subject or discovered by the Investigator. SAEs, NOCIs and MAAEs would be recorded as part of the collection of unsolicited AEs as specified in the visit procedures. Unsolicited AEs are collected separately from solicited AEs.

Solicited AEs continuing beyond 7 days will be identified using rules given in Section 5.2. They will not be presented in the summaries of unsolicited Adverse Events, but only in a Listing.

The definition of a treatment emergent AE (TEAE) is an event that occurs after vaccination and within the 30 days after vaccination (i.e., excluding those after a subject has given informed consent, but before vaccination):

- Onset (days) = Start date of AE – Date of Study Vaccine Administration + 1
- An AE is a TEAE if Onset \geq 1 and Onset \leq 30 and is not a continuing solicited AE

Adverse events are summarized by subject, therefore, in any tabulation, a subject contributes only once to the count for a given adverse event (SOC or preferred term).

Unsolicited AEs will be coded using the Medical Dictionary for Regulatory Activities (MedDRA) and will be summarized by decreasing frequency of SOC and preferred term within SOC in the control group, as follows:

- Unsolicited TEAEs
- Possibly or probably related unsolicited TEAEs
- Unsolicited TEAEs leading to study withdrawal

- SAEs
- Possibly or probably related SAEs
- NOCIs
- Possibly or probably related NOCIs
- MAAEs
- Possibly or probably related MAAEs
- AEs leading to death (only presented on the Safety Population overall)

Following summaries will be presented on the Safety Population overall only by decreasing frequency of PT, with an additional column “VAX-31” combining all subjects vaccinated with any dose of VAX-31:

- Unsolicited TEAEs
- Possibly or probably related unsolicited TEAEs

Following by-subject Listings will be provided:

- Pre-vaccination AEs (non-emergent)
- All unsolicited TEAEs
- All Serious post-vaccination AEs, NOCIs and MAAEs

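### The SAP takes prolonged solicited reactions out of the unsolicited-AE tables but has no rule for medically attended ones that resolve by Day 7, and read literally it drops prolonged, medically attended reactions from the SAE, NOCI and MAAE tables

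*Protocol*

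**What the plan says.** Protocol 8.1.3 sets the recording rule: "Solicited AE occurring or persisting beyond the solicitation period or which meet SAE/NOCI/MAAE criteria are also recorded as unsolicited AE". The second limb, on SAE, NOCI and MAAE criteria, carries no duration condition. Protocol 8.1.1 defines a medically attended event as "A new onset or worsening of a condition that prompts the subject to seek unplanned medical advice" in a physician's office, urgent care or emergency department, and makes no exception for diary symptoms. SAP 6.5.1.2 agrees on where such events are held: "SAEs, NOCIs and MAAEs would be recorded as part of the collection of unsolicited AEs as specified in the visit procedures".

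The SAP then separates the two kinds of event. In 6.5.1.2 an AE is a TEAE if its onset falls on Day 1 to 30 "and is not a continuing solicited AE". Under 5.2, continuing events "will be identified programmatically as all unsolicited adverse events with answer" Yes to the question "Is this a Prolonged Solicited Adverse Event". Section 6.5.1.2 adds that continuing events are left out of the unsolicited-AE summaries and shown by listing alone. Section 6.5.1.3 nevertheless gives them a table of their own and a table combined with the unsolicited TEAEs.

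The endpoint concerned is primary (SAP 3.2): "Percentage of subjects reporting unsolicited AE within 1 month after vaccination in each age group". Diary events from Day 1 to Day 7 feed the separate solicited endpoints (SAP 6.5.1.1).

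Two other protocol texts fit poorly with 8.1.3. Section 6.12 reads: "Unsolicited AE (any AE not listed in the diary) will be collected for this study". Section 8.5.1 mentions only solicited terms that fall outside or run past the collection window.

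**The concern.** The SAP removes one class of solicited reaction from the unsolicited tables and is silent on the other. Two reactions that differ only in duration and care-seeking are then handled in opposite ways: the short, medically attended one enters the primary unsolicited percentage, and the longer, unattended one does not.

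Two things are at stake. First, a reader comparing three dose levels with PCV20 could take a rise in unsolicited AEs as evidence independent of the solicited results, when part of it is the same events. The related unsolicited TEAE table has a smaller base, so a few such records would weigh more there, provided the unsolicited record is judged related. Second, the same sentence can err the other way. SAE, NOCI and MAAE percentages through 6 months are also primary endpoints, and their tables stand in the same list of unsolicited-AE summaries from which prolonged reactions are removed.

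**Working it through.** The plan states no figure on this point, so the check is of rules first and of size second.

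**Rule check.** TEAE = (1 ≤ onset ≤ 30) and (prolonged flag is not Yes).

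| Case | Flag | Solicited tables | Unsolicited TEAE | MAAE table, literal reading |
|---|---|---|---|---|
| A. Injection-site pain, onset Day 2, urgent-care visit Day 3, resolved Day 5 | No | counted | counted | counted |
| B. Same pain, no visit, lasting to Day 12 | Yes | counted | not counted | not an MAAE |
| C. Same pain, visit on Day 3, lasting to Day 12 | Yes | counted | not counted | not counted |
| D. New headache, onset Day 10, no visit | No | not counted | counted | not an MAAE |

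Case A is the gap in the unsolicited table. Case C is the gap in the MAAE table. It comes from the listing-only sentence and not from the TEAE definition, because the SAP does not restrict the SAE, NOCI and MAAE tables to TEAEs. Case D is properly unsolicited and should stay so. The flag value No in case A is inferred from the wording of the question; the CRF completion guidelines that SAP 5.2 cites are not among the documents.

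**Size.** Inputs:
- Arm size n = 250 (Protocol 10.3).
- Illustrative base b = 12.3%, the VAX-24 TEAE rate within 1 month (Protocol 2.1), taken as free of such duplicates. The documents do not say whether it is.
- m = share of subjects with a case A event. This is not in the documents. Assumed 1 to 3 per arm: 1/250 = 0.4%, 3/250 = 1.2%.

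Base count: 0.123 × 250 = 30.75, about 31 per arm.

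If no affected subject has another unsolicited AE, the percentage rises by 0.4 to 1.2 points. In relative terms that is 1/30.75 = 3% to 3/30.75 = 10%.

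If case A events are independent of other unsolicited AEs, the new rate is b + m(1 − b):
- m = 0.4%: 0.123 + 0.004 × 0.877 = 12.7%
- m = 1.2%: 0.123 + 0.012 × 0.877 = 13.4%
- wider assumed range, m = 0.2% to 3%: 12.5% to 14.9%

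Difference between arms, with 1 subject affected on PCV20 and 3 on one VAX-31 dose: (0.012 − 0.004) × 0.877 = 0.7 points.

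Related table, with an assumed base of 2% (0.02 × 250 = 5 subjects): 1 to 3 extra adds 20% to 60% relative. This holds only if every extra record is judged related and none of these subjects already has a related TEAE.

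Age groups: the minimum of 200 subjects aged 65 and older gives about 200/4 = 50 per arm, where one subject is 2 points.

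**The case against.** The strongest reply is that counting case A as unsolicited follows Protocol 8.1.3 to the letter. Nothing says the unsolicited endpoint must be free of reactogenicity; the protocol says only that the two types are collected separately. The parenthesis in Protocol 6.12 is shorthand and refers on to Section 8. No subject is counted twice within a table, and an early MAAE or SAE appears in the TEAE table as a matter of course. The safety tables are descriptive, the same rule applies to every randomized arm, and the events are listed by subject.

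Most of this stands. It shows that including case A is a permissible choice, but it does not explain why case B is treated the opposite way. The exclusion of continuing solicited AEs is itself an SAP addition: the TEAE definition in Protocol 8.1.1, which Protocol 10.6.3 says governs the summaries, does not contain it, and SAP 7 reports no changes. Having chosen separation, the SAP should apply it to both classes or say why not. The reply does not touch case C.

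Three stronger readings are tempting and are not supported:
- **Reactogenicity in general is counted again.** Only reactions that meet SAE, NOCI or MAAE criteria and resolve by Day 7 are. Protocol 8.1.1 narrows this further by asking for a diagnosis in place of symptoms where possible.
- **The related table is inflated automatically.** Protocol 6.11 sets the automatic probably-related value for solicited injection-site reactions. No text carries it to the unsolicited record, and systemic reactions are judged one by one.
- **The arm comparison is biased.** More medically attended reactions on one dose would be a real difference. The issue is which table it belongs in. Protocol 2.1 reports no apparent dose dependence for VAX-24, which points to a small contrast.

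**Conclusion.** The gap holds, within narrow limits. Protocol 8.1.3 creates two classes of solicited event on the unsolicited page, and the SAP has a rule only for the prolonged ones. As written, a medically attended reaction resolving by Day 7 counts in both the solicited and the unsolicited primary percentages, and in the related table if its unsolicited record is judged related. Read literally, the listing-only sentence also removes prolonged reactions meeting SAE, NOCI or MAAE criteria from those tables. A milder reading, that it refers only to the TEAE summaries, is possible, since SAP 6.5.1.3 does tabulate prolonged events; the text should settle which is meant.

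The effect is unknown and probably small: at most 0.4 to 1.2 points on the assumed 1 to 3 subjects per arm, and more visible in the related table and in subjects aged 65 and older. Both the care-seeking rate and the 2% related base are assumptions. No formal test depends on the result. The point is worth correcting because the endpoints are primary and the repair is cheap, not because it threatens the trial's conclusions.

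**What to change.** - **Flag.** In SAP 5.2 and 6.5.1.2, derive one flag for every unsolicited-page record that is a solicited term with onset on Day 1 to 7, whether prolonged or entered because it met SAE, NOCI or MAAE criteria. Identify it by matching term and onset to the eDiary. Records entered as a diagnosis will not match by term, so say how they are handled.
- **TEAE tables.** Exclude flagged records from the unsolicited TEAE and related unsolicited TEAE tables.
- **SAE, NOCI and MAAE tables.** Keep every flagged record that qualifies, including prolonged ones, and list all flagged records.
- **Combined table.** State in SAP 6.5.1.3 how flagged records enter. Case A now reaches that table only as an unsolicited TEAE and would otherwise drop out.
- **Consistency.** Reconcile Protocol 6.12, 8.1.3 and 8.5.1, and declare the change in SAP 7.

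The cost is SAP wording, one derived variable and the reconciliation of those protocol sections; no new data are needed. The downside is a slightly lower, and so less conservative, unsolicited percentage. The events stay visible in the solicited tables and in the SAE, NOCI and MAAE tables.

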### **8.1.4 Serious Adverse Event**

An SAE is an AE (either solicited or unsolicited) which meets any of the following criteria:

- Results in death
- Is life-threatening
- Requires hospitalization or prolongs an existing hospitalization
- Results in a persistent or significant incapacity or substantial disruption of the ability to conduct normal life functions
- Is a congenital anomaly or birth defect
- Important medical event that may jeopardize the patient or subject and/or may require medical or surgical intervention to prevent any of the above outcomes

The Investigator will evaluate all AE for seriousness using the above criteria.

“Life-threatening” means that in the opinion of the Investigator the subject was at immediate risk of death from the event as it occurred. It does not mean that the event might have caused death had it occurred in a more severe form.

Hospitalization for observation or for elective treatment of a pre-existing condition that did not worsen during the study is not considered an SAE.

Important medical events may be considered serious at the discretion of the Investigator.

These seriousness criteria also apply to the Study Stopping Rules in Section [8.10](#).

